3.0 TERMS AND DEFINITIONS (CONTINUED)

SAEs (Continued)	
 3. Inpatient Hospitalization or Prolongation of existing hospitalization 4. A Persistent or Significant Incapacity or a substantial disruption in the ability to conduct normal life functions, or 5. Congenital Anomaly or Birth Defect. 6. Important medical events that may not result in death, be life-threatening or require hospitalization, may be considered serious when based upon appropriate medical judgement they may jeopardize the patient or may require medical or surgical intervention to prevent one of the outcomes listed in this definition.
SaO₂	Arterial oxygen saturation
SpO₂	Arterial oxygen saturation measured by pulse oximetry
Submassive PE	A normotensive patient with PE and evidence of RV dysfunction.
SvO₂	Venous oxygen saturation
Troponin I	Cardiac troponins are the most sensitive and the most specific biochemical markers showing myocardial injury. Elevated troponin can also be seen in acute pericarditis, myocarditis, acute PE, severe cardiac failure, sepsis and acute renal failure as well as in myocardial infarction. In acute PE, the mechanic load of the right ventricle is increased because of the increased pulmonary vascular resistance following pulmonary artery obstruction. That can lead to acute right ventricular dilatation. The dilatation and hypokinesia of the right ventricle may cause severe myocardial ischemia and increase the troponin levels. Increased serum cTnI levels support the diagnosis of severe PE.

4.0 BACKGROUND AND RATIONALE

4.1 Clinical Problem

Acute venous thromboembolism (VTE) includes deep vein thrombosis (DVT) and acute pulmonary embolism (PE). PE occurs when a deep vein thrombus breaks loose and embolizes to the pulmonary artery. Pulmonary embolism is the third leading cause of cardiovascular death after myocardial infarction and stroke and is a major global health problem.^{1,2}

Raskob et al (2014) conducted a literature search and review and found that there is a strong and consistent association between an increase in incidence of VTE and increasing age. They found the annual incidence increased from between 2 and 7 per 1,000 population for those 79 and younger to between 3 and 12 per 1,000 population for those aged 80 and older. This finding has major implications for the treatment of the elderly in the US healthcare system.² It is important to note that 60 percent of the VTE events are associated with hospitalization.³ The number of deaths from VTE in the USA has previously been reported to be approximately 300,000 annually.^{3,4} Clinically, patients may present with DVT or PE, or both. With many of the known risk factors, advanced age, immobility, surgery, obesity, increasing in our society, this number only continues to grow. Because there is no national surveillance program for VTE, the precise number with VTE of all types is unknown.^{5,6}

Patients who present with PE may be classified into low risk, intermediate risk (submassive) or high risk (massive) PE. Both massive and submassive PE cause right ventricular (RV) dysfunction, while massive PE in addition causes systemic hypotension. Typical diagnostic studies include contrast enhanced computerized tomography (CT) to diagnose the PE, echocardiography to assess right and left ventricular function, and cardiac biomarkers, such as troponin I, and BNP to assess the degree of myocardial ischemia/strain associated with the PE. Patients categorized as having a low-risk PE do not have evidence of hemodynamic compromise or RV dysfunction. Low risk PE patients are not included in this study for obvious reasons.⁷

4.2 Current Treatment Options

Anticoagulant therapies are administered to symptomatic patients while their work-ups are being completed for a definitive diagnosis of massive or submassive PE. For the treatment of massive and submassive PE, both systemic administration and catheter-directed administration of thrombolytic therapies have been utilized.⁸⁻¹⁰ However, systemic administration of thrombolytics carries a prohibitively high risk of bleeding: Up to 7% intracranial bleeds and up to 20% major bleeding rates; hence the attraction of delivering thrombolytics in much lower dosage directly into the clot to treat this potentially life-threatening condition.¹¹

Devices for percutaneous treatment of patients in whom systemic thrombolytic therapy is absolutely contraindicated have been developed and utilized. The percutaneous devices include manual thrombus fragmentation using a balloon dilatation catheter or a pigtail (off-the shelf technologies). More recently, catheters specifically created for thrombus fragmentation that produce greater fragmentation of the clot compared to off-the-shelf technologies mentioned

previously, without aspirating the clot; aspiration or suction thrombectomy devices to decrease thrombus burden; rheolytic thrombectomy where a saline jet is directed into the clot and the clot and saline are aspirated, have been introduced.^{7-10,12-14} However, there are also hazards associated with rapid clot fragmentation including hemodynamic collapse due to the distal embolization of thrombus and release of vasoactive substances.

Over the past several years a device received 510(k) clearance for its ultrasound-facilitated, catheter directed low-dose fibrinolysis using r-tPA (EKOS, Bothell WA). With this technology, the EKOS ultrasound device was used to deliver t-PA in patients with massive and submassive PE at 1mg/hour over 24 hours (unilateral PE), and 2mg/hour over 12 hours (bilateral PE). This treatment methodology achieved an absolute reduction in RV:LV ratio of 0.42 (± 0.36), the mean baseline was 1.55 (± 0.39) and at 48 hours 1.13 (± 0.2).^{15,17}

While it is critical to reduce RV/LV ratio, it is of great importance to both short-term and long-term patient outcomes to decrease the thrombus burden as much as is feasible. Even a small reduction in the clot burden can translate into a marked improvement in RV function and improve acute survival. However, much more effective reduction in the residual clot burden is required to reduce the long-term complications of PE, including disabling post-PE syndrome and chronic thromboembolic pulmonary hypertension (CTEPH).⁷

4.3 Study Rationale

While the medical community continues to focus on prevention of VTE, half of all VTE patients have unprovoked VTE. Therefore, the treatment options for patients who present with DVT and/or acute PE must continue to evolve to increase efficacy, decrease side effects, limit long-term complications, and provide an improved quality of life for these patients. This study is focused on the treatment of patients with acute submassive PE with an interventional device designed to increase the exposure of the thrombus burden to endogenous and exogenous thrombolytics, thus this increased exposure has the potential to greatly decrease the thrombus burden.

The Bashir™ Endovascular Catheter has been designed to administer therapeutic agents in the peripheral vasculature. Because of the unique design of the catheter, with its six expandable infusion limbs, the Bashir™ Endovascular Catheter has the ability to: 1. Create a much larger central channel for blood flow, thereby utilizing the body's own endogenous fibrinolytic agents to lyse the clot, and 2. Greatly enhance the radial dispersion of a catheter-administered thrombolytic agent throughout the thrombus. Expansion of the multiple arms of the basket in the infusion catheter causes fissuring of the clot. The net result is that a greater surface area of clot is exposed to both endogenous and exogenously administered lytic agents, thereby promoting clot dissolution.

This first-in-man study will utilize the Bashir™ Endovascular Catheter to administer catheter directed thrombolysis in patients with submassive PE who have consented and meet all eligibility criteria. The Bashir™ catheter represents a new methodology for localized catheter-based delivery of thrombolytics. The thrombolytic to be used in this study is r-tPA (Genentech

Corporation, South San Francisco, USA).¹⁶ The dosing of the thrombolytic in the past has been much greater than what is proposed in this study. The SEATTLE II study administered a total of 24 mg of r-tPA over 12 hours for bilateral PE and 24mg over 24 hours for unilateral PE. The incidence of major bleeding in the SEATTLE II study was 10 percent.¹⁷ The design of the Bashir Endovascular Catheter with the multiple infusion limbs creating a basket-like formation when expanded, provides a greater surface area in the thrombus for the endogenous and exogenous thrombolytics to take effect, as described above.

Because of the rationale stated previously, a reduced dose of thrombolytic can be administered over a reduced period of time due to an increased exposure of the clot to endogenous and exogenous thrombolytics for clot dissolution. The Optalyse study, using the EKOS catheter, presented at ISET, February 6, 2018, was conducted to assess the outcomes with lower dose r-tPA administration for the treatment of acute submassive PE. Four groups were administered lower doses of r-tPA over a shorter period of time. While each group showed a statistically significant reduction in RV/LV ratio at 48 hours post-procedure, the reduction in residual clot burden was noticeably lower (6%) in patients treated with the smallest dose of r-tPA for the shortest time period (4/8 mg r-tPA over 2 hours) compared to those treated with the highest dose for the longest duration (26% reduction in clot burden; 12/24 mg r-tPA over 6 hours). This illustrates the discordance between reduction in RV/LV diameter ratio and reduction in clot burden. It is much easier to achieve the former than the latter with low doses of r-tPA for shorter periods of time. There is clearly also a lot of room for improvement if 74% of the clot burden still remains after the highest dose of infusion in the OPTALYSE study.¹⁸

We hypothesize that the dose of r-tPA may be reduced using the Bashir™ Endovascular Catheter from what was administered in the SEATTLE II study, i.e. 24mg over 12 hours (bilateral PE) or 24 hours (unilateral PE), because of its unique features described previously.¹⁷ We therefore propose to utilize the following regimen: r-tPA 2mg in 20 cc administered in 1mg and 10cc increments x 2 into the PA for a total of 2 pulse sprays into the infusion basket via its infusion port on the handle, using a syringe, followed by a 10mg infusion at 1.27mg per hour until complete for unilateral PE, and 5mg infusion into each pulmonary artery for bilateral PE, at 0.65mg/hour until complete for a total dose of 1.3mg/hour for bilateral PE. This is a total of 12 mg over approximately 8 hours (pulse spray 1mg x 2 sprays = 2mg plus infusion at 1.27mg/hour x 7.87 hours (approximately 8 hours = 12mg) for unilateral PE. For bilateral PE, we propose to administer the same pulse spray and one-half of the infusion dose into each PA to total the unilateral infusion dose, for a total of 14mg administered including the pulse sprays and the infusions. This is a substantially lower dose and a shorter duration of treatment compared to SEATTLE II for the treatment of PE in a similar patient cohort. Additionally, an efficacy study stopping rule has been established for this study based on the reduction in RV:LV diameter ratio observed in the SEATTLE II study (0.42-0.36). The minimal reduction of 0.06 in SEATTLE II formed the basis for the efficacy study stopping rule for this study. If a reduction is less than 0.06 (refer to Section 18.3) in the first three patients, the study will be paused to re-evaluate the r-tPA dosage and administration.

5.0 INVESTIGATIONAL DEVICE

The Bashir™ Endovascular Catheter is a device intended for the localized infusion of therapeutic agents into the pulmonary artery and peripheral vasculature. The distal infusion segment of the device contains an expandable and retractable radial array of conduits with multiple laser drilled orifices used for the delivery of the therapeutic agents at multiple cross-sectional points of the target vessel location. The infusion segment can be expanded and collapsed by the actuator (slider) located on the handle at the proximal end of the device. The infusion line connector is also located on the handle.¹⁹

Figure 1. Bashir Endovascular Catheter

[figure not shown]

Figure 2. Bashir Endovascular Catheter with Basket Expanded

[figure not shown]

Table 1. Bashir™ Endovascular Catheter Dimensions

French Size	7 F (2.3 mm)
Effective Length	92.5 cm (35.44 in)
Infusion Segment Length	12.50 cm (4.92 in)

6.0 STUDY DESIGN

6.1 Study Objective

Assess the safety and feasibility of the Bashir™ Endovascular Catheter for the administration of low dose thrombolysis for acute submassive pulmonary embolism.

6.2 Primary and Secondary Endpoints

The primary endpoints below are appropriate for a first-in-man study. The secondary endpoints are for the purpose of additional safety assessments, additional procedure data related to any device issues (if any), and initial efficacy parameters.

6.2.1 Primary Endpoints

1. Safety: Major bleeding, as defined by International Society of Thrombosis and Hemostasis (ISTH), within 72 hours of initiation of r-tPA administration. Bleeding criteria are as follows: Major Bleeding in Non-Surgical Patients.
 - a. Fatal bleeding; and/or
 - b. Symptomatic bleeding in a critical area or organ, such as intracranial, intraspinal, intraocular, retroperitoneal, intraarticular or pericardial, or intramuscular with compartment syndrome; and/or
 - c. Bleeding causing a fall in hemoglobin level of 2g/dL (1.24mmol/L) or more or leading to transfusion of two or more units of whole blood or red cells.²³
2. Feasibility: Device success defined as the ability to use the Bashir™ Endovascular Catheter as per this protocol.

6.2.2 Secondary Endpoints

1. All-cause mortality at hospital discharge through 30-day follow-up.
2. SAEs through 30-day follow-up.
3. Anticipated (non-serious) adverse events (AEs) through 30-day follow-up.
4. Recurrent PE through 30-day follow-up.
5. Clinically Relevant Non-Major bleeding: Any sign or symptom of hemorrhage (e.g. more bleeding than would be expected for a clinical circumstance, including bleeding found by imaging alone) that does not fit the criteria for the ISTH definition of major bleeding but does meet at least one of the following criteria:
 - a) Requiring medical intervention by a healthcare professional.
 - b) Leading to hospitalization or increased level of care.
 - c) Prompting a face to face (i.e., not just a telephone or electronic communication) evaluation.
6. Technical procedural complications.
7. RV/LV end diastolic diameter ratio at 24 hours after completion of r-tPA infusion compared to baseline, by echocardiogram.

8. RV/LV diameter ratio at 48 hours after completion of r-tPA infusion, by contrast enhanced chest CTA compared to baseline.
9. Modified Miller Index at 48 hours post r-tPA infusion as compared to baseline by contrast enhanced chest CTA.
10. Systolic PA pressure measured at completion of infusion and compared to baseline.
11. Cardiac output (CO by modified Fick calculation) and cardiac index (CI) following completion of the r-tPA infusion compared to the baseline. Please refer to Terms and Definitions section for the modified Fick calculation to be done in the IR suite/Cath lab.

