11.1 Assessments

1. **Physical Examination** – The physician will perform a physical exam at 30-day follow-up visit (± 7 days).
2. **AEs/ SAEs** – All adverse events will be recorded at the 30-day follow-up visit.

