12.0 ANTICIPATED ADVERSE EVENTS

The following events are anticipated adverse events in subjects who are treated for pulmonary embolism. An adverse event is any untoward medical occurrence associated with the use of a drug in humans, whether or not considered drug related (21 CFR 312.32(a)).

Suspected adverse reaction means any adverse event for which there is a reasonable possibility that the drug caused the adverse event. For the purposes of IND safety reporting, ‘reasonable possibility’ means there is evidence to suggest a causal relationship between the drug and the adverse event. A suspected adverse reaction implies a lesser degree of certainty about causality than adverse reaction, which means any adverse event caused by a drug. A suspected adverse reaction is an adverse event where there is a reasonable possibility the drug caused the adverse event. The sponsor is responsible for making the causality.

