13.0 ADVERSE EVENT REPORTING

13.1 Serious Adverse Events and Serious Suspected Adverse Reactions

Serious adverse events (SAE) or serious suspected adverse reaction (SUSAR) must be reported to the study manager within 24 hours of knowledge of the event.

Serious adverse event or serious suspected adverse reaction: An adverse event or suspected adverse reaction is considered "serious" if, in the view of either the investigator or sponsor, it results in any of the following outcomes:

1. Death;
2. A life-threatening adverse event;
3. Inpatient hospitalization or prolongation of existing hospitalization;
4. A persistent or significant incapacity or substantial disruption of the ability to conduct normal life functions, or a congenital anomaly/birth defect;

5. Important medical events that may not result in death, be life-threatening, or require hospitalization may be considered serious when, based upon appropriate medical judgment, they may jeopardize the patient or subject and may require medical or surgical intervention to prevent one of the outcomes listed in this definition.

The following event definitions, as defined in 21 CFR 312.32(a) will be reported as serious adverse events and the reporting requirements above must be followed.

Life-threatening adverse event (or life-threatening suspected adverse reaction): An adverse event or suspected adverse reaction is considered "life-threatening" if, in the view of either the investigator or sponsor, its occurrence places the patient or subject at immediate risk of death. It does not include an adverse event or suspected adverse reaction that, had it occurred in a more severe form, might have caused death.

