13.2 Unexpected Adverse Event or Unexpected Suspected Adverse Reaction

The following event definitions, as defined in 21 CFR 312.32(a) will be reported as serious adverse events and the reporting requirements above must be followed.

An Adverse Event or Suspected Adverse Reaction is considered "unexpected" if it is not listed in the investigator brochure or is not listed at the specificity or severity that has been observed; or, if an investigator brochure is not required or available, is not consistent with the risk information described in the general investigational plan or elsewhere in the current application, as amended.

It is anticipated that no unexpected adverse reactions will occur as r-tPA is FDA approved for the treatment of pulmonary embolism. The currently approved labeling requires 100mg of r-tPA to be administered intravenously over two (2) hours. This is 86mg more than the maximum dose required in this protocol administered over two (2) hours, not over approximately eight (8) hours as in this protocol.

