13.3 Adverse Event Documentation

All adverse events (AEs) including those categorized as anticipated, life threatening, serious, unexpected, and suspected are to be reported on the case report form.

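### Secondary endpoint 3 leaves out non-serious adverse events that are not on the anticipated list, and Section 13.2 read literally would count some of them as serious

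*Combined protocol and SAP*

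**What the plan says.** Section 6.2.2 lists eleven secondary endpoints. Item 2 is "SAEs through 30-day follow-up" and item 3 is "Anticipated (non-serious) adverse events (AEs) through 30-day follow-up". The synopsis carries the same restriction, so it is not a slip in one place.

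Section 12.0 gives the meaning of anticipated: "The following events are anticipated adverse events in subjects who are treated for pulmonary embolism". The events are then listed in Tables 3 (device), 4 (r-tPA) and 5 (procedure).

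Sections 3.0 and 13.1 define seriousness by outcome. An event is serious if, in the view of the investigator or sponsor, "it results in any of the following outcomes": death, threat to life, hospitalization or its prolongation, incapacity, congenital anomaly, or an important medical event. Being unexpected is not on the list.

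Section 13.2 says that the definitions following its opening sentence "will be reported as serious adverse events and the reporting requirements above must be followed". The only definition that follows is that of unexpected, which applies "if it is not listed in the investigator brochure or is not listed at the specificity or severity that has been observed". If no brochure is required or available, the reference is the risk information elsewhere in the application. No seriousness condition is attached.

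On collection, Section 13.3 states: "All adverse events (AEs) including those categorized as anticipated, life threatening, serious, unexpected, and suspected are to be reported on the case report form". Section 11.1 adds: "All adverse events will be recorded at the 30-day follow-up visit". Section 16.2 provides for descriptive summaries of the collected data and MedDRA coding of adverse events.

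**The concern.** Endpoints 2 and 3 look as if they should together cover every adverse event, split by seriousness. They do not, because the word anticipated removes part of the non-serious half. Section 13.2 then uses expectedness, which concerns prior knowledge, as if it were seriousness, which concerns outcome.

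This matters more here than in a late-phase study. In a first-in-man device study, events that nobody listed beforehand are the new safety information. Section 13.2 expects no unexpected reactions because r-tPA is an approved drug, but that argument does not extend to the new catheter. Section 16.1 says the results will help refine endpoints for a larger pivotal trial, so an unclear classification could carry forward. SAE status also has a practical effect: under Section 18.4.1 a suspected device-caused SAE leads to adjudication by the data safety monitor (DSM), return of the device, a root cause analysis and a decision on whether the study continues.

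**Working it through.** The plan gives no computed figure on this point, so the check sets the definitions side by side.

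**Inputs**
- Anticipated: listed in Tables 3 to 5 (Section 12.0).
- Unexpected: not in the investigator brochure, or not at the observed specificity or severity (Section 13.2).
- Serious: meets an outcome criterion (Sections 3.0 and 13.1).
- Endpoints 2 and 3 (synopsis and Section 6.2.2).
- Sample size: up to 10 (synopsis; Section 16.1).

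Anticipated and unexpected refer to different lists, so they are not opposites and must be crossed.

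| Serious by outcome? | In Tables 3 to 5? | Expected per brochure? | Endpoint by the outcome definition | Endpoint if 13.2 is read literally |
|---|---|---|---|---|
| Yes | either | either | 2 | 2 |
| No | Yes | Yes | 3 | 3 |
| No | Yes | No | 3 | 2 |
| No | No | Yes | neither 2 nor 3 | neither 2 nor 3 |
| No | No | No | neither 2 nor 3 | 2 |

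**Reading the table**
1. Serious events are always placed correctly.
2. A non-serious event outside Tables 3 to 5 but in the brochure is in neither adverse-event endpoint, however Section 13.2 is read.
3. A non-serious event outside both lists is in neither endpoint under the outcome definition. Under the literal reading of Section 13.2 it is in endpoint 2 without meeting any seriousness criterion.
4. A non-serious event in the tables but unexpected under the brochure, for example at a greater severity than the brochure describes, moves from endpoint 3 to endpoint 2 under the literal reading.
5. In rows four and five the event is still counted if it qualifies under endpoint 4 (recurrent PE), 5 (clinically relevant non-major bleeding) or 6 (technical procedural complications).

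The affected rows are not empty by construction. Headache and nausea, for example, appear in none of Tables 3 to 5.

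**Size**

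The subject-level SAE rate is (subjects with at least one SAE) / n. One subject with no true SAE, counted as having one, adds 1/n. With n = 10 this is 1/10 = 10 percentage points. Since the plan enrolls up to 10, the step is at least that large. The documents give no expected frequency for such events, so the number of affected subjects cannot be estimated.

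**The case against.** The case for leaving the text alone is substantial.

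- **Reporting route only.** Section 13.2 sits in the chapter on reporting, and its sentence goes on to invoke the reporting requirements. It can be read as sending unexpected events down the SAE reporting route without reclassifying them. The same lead-in stands in Section 13.1 before the definition of life-threatening, where it fits, which suggests a carried-over sentence. This reading is reasonable, but the text says reported as serious, and nothing there separates reporting from counting. It also does nothing for the gap in endpoint 3.
- **Central adjudication.** Section 17.0 gives the DSM final adjudication of all types of adverse events. A reader might infer that sites will classify differently and that the differences will reach the results. The documents do not support that as a prediction, because a site's label is not final. Still, no rule in the protocol tells the DSM which text governs.
- **Small affected group.** Tables 3 to 5 are broad, covering among others pain, fever, anemia, arrhythmia, infection and hypotension. The group may well be small, but the brochure is not among the documents, so this cannot be checked.
- **No decision depends on an SAE rate.** The primary endpoints are major bleeding and device success. Section 18.2 counts deaths and intracranial hemorrhages, Section 18.3 uses the RV/LV ratio, Section 18.4.2 counts device failures, and Section 18.4.1 works event by event. This stands, and it is the main reason for the minor grading.

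Two stronger readings are tempting. One is that unanticipated non-serious events disappear from the study or from every endpoint. They do not: Sections 13.3 and 11.1 capture them, Section 16.2 covers their descriptive summary, and some count under endpoints 4 to 6. The other is that the safety summary must come out wrong. That does not follow, since a general descriptive listing of all adverse events would show these events whatever the endpoint wording.

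**Conclusion.** The point holds as a defect of endpoint definition and event classification: wrong as written, minor severity. Endpoint 3 excludes non-serious events outside Tables 3 to 5, and this follows from the text without further assumption. The misplacement into endpoint 2 depends on reading Section 13.2 literally; on the reporting-route reading it does not occur. Where it does occur, each affected subject with no other SAE moves the subject-level SAE rate by 10 percentage points at n = 10. Section 16.2 sets no rule for tabulating unanticipated non-serious events, so the analysis text does not close the gap. No primary endpoint, sample size or rate-based stopping rule is affected; the only operational effect would be a possible unneeded review under Section 18.4.1.

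**What to change.** 1. In the synopsis and Section 6.2.2, define endpoint 3 as all non-serious adverse events through 30-day follow-up, tabulated separately as anticipated (Tables 3 to 5) and unanticipated.
2. Reconcile Section 13.2 with Sections 3.0 and 13.1: record expectedness as an attribute separate from seriousness, and state that only events meeting the Section 13.1 criteria count in endpoint 2. Leave the existing reporting route for unexpected events in place.
3. State that anticipated refers to Tables 3 to 5 and unexpected to the investigator brochure, so that the two terms are not used interchangeably in the tables.

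The cost is wording only. Section 13.3 already puts every adverse event on the case report form, so event collection and the sample size do not change.
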